#### **9.5 Study Size**

The primary endpoint of this study is to investigate the effectiveness of adalimumab in Korean patients with Ulcerative Colitis (UC) in real life settings.

With reference to adalimumab real life data in UC, clinical response rate to adalimumab at week 12 was about 75%. Assuming 95% confidence interval, 15% confidence interval width and an estimated drop-out rate of 5%, we aim to recruit up to 147 subjects in this study.

## **9.6 Data Management**

Investigator should complete, sign and date the CRFs accurately. All CRFs must be legible and completed in indelible ballpoint ink. Corrections to the CRFs should be made with a single line, be initialed and dated, with the reason for changes given. Data are not to be obliterated by blacking out, correction fluid, or by erasing the original entry.

At the completion of the study, the completed signed and dated case report forms of all enrolled subjects should be provided to AbbVie by the investigator. ONLY data specified in the protocol should be collected and submitted to AbbVie.

CRA's or their designees will be responsible to review the collected case report forms for completeness and conclusiveness.

## **9.7 Data Analysis**

The study population will be classified by ITT (Intend-To-Treat) set and PP (Per-Protocol) set.

-ITT set: The ITT set will include all subjects intended to treat with adalimumab. At week 8, all subjects who have received adalimumab treatment at least once will be included and, at week 56, all subjects who have clinical response at week 8 will be included.

-PP set: The PP set will include all subjects who meet the eligibility criteria for this study and complete the evaluation without any major protocol deviation among the ITT set. At week 8, all subjects who meet the eligibility criteria and complete the evaluation at week 8 will be included and at week 56, all subjects who complete the evaluation and the study follow-up without any major protocol deviation.

## **General Considerations**

Continuous variables will be described with the number of subjects, arithmetic mean and standard deviation. For categorical variables, the frequency and proportion will be presented. The values such as arithmetic mean, standard deviation, and proportion will be

rounded to two decimal places. If the observation value is missing value, it will be treated as a missing value in the analysis.

### **Baseline Characteristics including demographics**

Descriptive statistics will be used to present variables regarding demographics and disease/medication related data. Continuous variables will be described with the number of subjects, arithmetic mean and standard deviation. For categorical variables, the frequency and proportion will be presented. The values such as arithmetic mean, standard deviation, and proportion will be rounded to two decimal places.

If the observation value is missing value, NRI and LOCF will be used for a missing value. Statistical analyses will be performed using SAS V9.2 or higher.

### **Primary Endpoint:**

- The percentage of subjects with clinical response at week 8
- The percentage of subjects with clinical response at week 56 in in week 8 responders

; The frequency and proportion of subjects with clinical response at week 8 and 56 will be presented.

### **Secondary Endpoints:**

- The percentage of subjects with clinical remission at week 8 and 56 (in week 8 responders)

; The frequency and proportion of subjects with clinical remission at week 8 and 56 will be presented.

- The percentage of subjects with steroid-free remission at week 8 and 56 (in week 8 responders)

; The frequency and proportion of subjects with steroid-free remission at week 8 and 56 will be presented.

- The percentage of subjects with mucosal healing at week 8 and 56 (in week 8 responders)

; The frequency and proportion of subjects with mucosal healing at week 8 and 56 will be presented.

- The change of partial Mayo score from baseline overtime

; The descriptive statistics (the number of patients, mean, standard deviation, min, max) for partial Mayo score according to study visit and the change from baseline overtime will be presented.

- The change of the composition of Fecal micro biota from baseline at week 56
- The mean change of Fecal calprotectin level from baseline at week 56

### **9.7.1 Safety Analysis**

The serious adverse event · adverse drug reaction will be coded by MedDRA latest version.

The cumulative total number and percentage of subjects reporting serious adverse event · adverse drug reaction will be tabulated. Also, AEs leading to discontinuation of adalimumab will be collected and tabulated.

### **9.7.2 Exploratory Analysis**

In addition to the above secondary end-points, exploratory analysis will focus on identifying potential predictive factors of clinical effectiveness of adalimumab. These would include age, disease duration, disease extent, ESR and CRP concentrations, level of hemoglobin, albumin level, Fecal calprotectin level and the composition of Fecal

microbiota at baseline and week 8 trough levels of adalimumab at week 8, TNF antagonist naivety will be considered.

## **9.8 Quality Control**

Prior to the initiation of the study, an investigator's meeting or initiation visit will be held with AbbVie personnel or his/her designee, the investigators and their study coordinators. This meeting will include a review of the protocol and CRF completion guideline.

Investigator must assure that the study is conducted in accordance with the protocol and all relevant regulations and CRF is completed accurately.

In general, monitoring for any site is not required, but, for quality assurance, internal consistency check for completeness and consistency of data will be done to ensure the integrity of the information reported.

CRF will be reviewed by CRAs at AbbVie or their designees for completeness and conclusiveness and when necessary, query will be generated and will be resolved by the site staffs.

All data hand-entered in the database will be verified by a double-key entry procedure. Any discrepancies will be reviewed against the hard copy CRF and corrected. After completion of the entry process, computer logic checks will be run. Any necessary corrections will be made to the database and documented.

## **9.9 Limitations of the Research Methods**

NA

## **9.10 Other Aspects**

NA

## **10.0 Protection of Human Subjects**

The study should receive approval from the Institutional Review Board (IRB) of the each institution, and then a written study agreement should be made with institutions before the initiation of the study in each institution.

Patient written authorization form to use and/or disclose personal and/or health data from subjects must be obtained prior to enrolling the subject and the investigator is required to document this authorization.

Subject confidentiality must be maintained at all times; therefore demographics that could identify the patients will not be collected.

Monitoring for any sites is not required. However internal consistency check for completeness and consistency of data will be done to ensure integrity of the information reported.

## **11.0 Management and Reporting of Complaints**

A Complaint is any written, electronic, or oral communication that alleges deficiencies related to the physical characteristics, identity, quality, purity, potency, durability, reliability, safety, effectiveness, or performance of a product/device after it is released for distribution.

The investigational product in this trial contains both:

- Biologic compound(s) and
- Device component(s) (pre-filled syringe, pen).

Complaints associated with any component of this investigational product must be reported to the Sponsor (Section 11.2.2). For adverse events, please refer to Sections 11.1.1 through 11.1.6. For product complaints, please refer to Section 11.2.

## 11.1 Medical Complaints

### 11.1.1 Adverse Event Definition and Serious Adverse Event Categories

An adverse event (AE) is defined as any untoward medical occurrence in a patient, which does not necessarily have a causal relationship with their treatment. An adverse event can therefore be any unfavorable and unintended sign (including an abnormal laboratory finding), symptom, or disease temporally associated with the use of a medicinal product, whether or not the event is considered causally related to the use of the product.

Such an event can result from use of the drug as stipulated in the labeling, as well as from accidental or intentional overdose, drug abuse, or drug withdrawal. Any worsening of a pre-existing condition or illness is considered an adverse event.

If an adverse event meets any of the following criteria, it is considered a serious adverse event (SAE):

Death of Patient:	An event that results in the death of a patient.
Life-Threatening:	An event that, in the opinion of the investigator, would have resulted in immediate fatality if medical intervention had not been taken. This does not include an event that would have been fatal if it had occurred in a more severe form.
Hospitalization:	An event that results in an admission to the hospital for any length of time. This does not include an emergency room visit or admission to an outpatient facility.
Prolongation of Hospitalization:	An event that occurs while the study patient is hospitalized and prolongs the patient's hospital stay.
Congenital Anomaly:	An anomaly detected at or after birth, or any anomaly that results in fetal loss.
Persistent or Significant	An event that results in a condition that substantially interferes with the activities of daily living of a study

Disability/Incapacity:	patient. Disability is not intended to include experiences of relatively minor medical significance such as headache, nausea, vomiting, diarrhea, influenza, and accidental trauma (e.g., sprained ankle).
Important Medical Event Requiring Medical or Surgical Intervention to Prevent Serious Outcome:	An important medical event that may not be immediately life-threatening or result in death or hospitalization, but based on medical judgment may jeopardize the patient and may require medical or surgical intervention to prevent any of the outcomes listed above (i.e., death of patient, life threatening, hospitalization, prolongation of hospitalization, congenital anomaly, or persistent or significant disability/incapacity). Additionally, any elective or spontaneous abortion or stillbirth is considered an important medical event. Examples of such events include allergic bronchospasm requiring intensive treatment in an emergency room or at home, blood dyscrasias or convulsions that do not result in inpatient hospitalization, or the development of drug dependency or drug abuse.

### 11.1.2 Severity

The following definitions will be used to rate the severity for any adverse event being collected as an endpoint/data point in the study and for all serious adverse events.

Mild:	The adverse event is transient and easily tolerated by the patient.
Moderate:	The adverse event causes the patient discomfort and interrupts the patient's usual activities.
Severe:	The adverse event causes considerable interference with the patient's usual activities and may be incapacitating or life threatening.

### **11.1.3 Relationship to Pharmaceutical Product**

The following definitions will be used to assess the relationship of the adverse event to the use of product:

- Reasonable Possibility** An adverse event where there is evidence to suggest a causal relationship between the product and the adverse event.
- No Reasonable Possibility** An adverse event where there is no evidence to suggest a causal relationship between the product and the adverse event.

If no reasonable possibility of being related to product is given, an alternate etiology must be provided for the adverse event.

### **11.1.4 Serious Adverse Event Collection Period**

Serious adverse events will be reported to AbbVie from the time the physician obtains the patient's authorization to use and disclose information (or the patient's informed consent) until 70 days following the intake of the last dose of adalimumab taken during the study.

### **11.1.5 Serious Adverse Event Reporting**

This protocol requires all SAEs as outlined in protocol section 11.1.1 to be actively solicited. The safety profile of adalimumab which has over 3.5 million PYs of post-marketing exposure is stable and well established; non-serious events will not be actively solicited as these events are not likely to contribute to the further understanding of the safety profile of the product. Any non-serious AEs will be collected as spontaneous reports if AbbVie is notified.

In the event of a serious adverse event, and additionally, any non-serious event of malignancy in patients 30 years of age and younger, whether related to study drug or not,

the physician will notify the AbbVie contact person identified below within 24 hours of the physician becoming aware of the event.

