### **9.2.2 Drop-Out Subjects**

Once a subject is dropped out from the study, no further information for that subject will be collected. However, the reason for drop-out will be reported and serious adverse events will be reported to AbbVie until 70 days following the intake of the last dose of adalimumab.

Subjects will be dropped out from the study:

- 1) If the subjects choose to withdraw from the study
- 2) Where ethical or practical conflicts hinder the procedure of the study, and such cases will be determined based on the investigator's judgment
- 3) In case of Adalimumab discontinuation at any point during study period

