#### **Blood samples**

Trough levels of adalimumab will be measured at week 8 and at the time of inadequate

response despite dose escalation. Antibodies against adalimumab (AAA) will be measured at inadequate response despite dose escalation. Inadequate response is defined as: (1) partial Mayo score equal to or above baseline score on 2 consecutive visits at least 14 days apart (for patients with a partial Mayo score of 4-7 at baseline); (2) partial Mayo score  $\geq 7$  on 2 consecutive visits at least 14 days apart (for patients with a partial Mayo score of 8 or 9 at baseline). In case of inadequate response, subjects will move to 40 mg every week. Unresponsive subjects to dose escalation will discontinue on their physician's judgement.

In the event of adalimumab discontinuation, the reason for discontinuation will be collected.

In the analyses of each individual predictive factors, subjects of various ages, disease duration, disease extent, ESR and CRP concentrations, level of hemoglobin, albumin level, Fecal calprotectin level and the composition of Fecal microbiota at baseline and week 8, trough levels of adalimumab at week 8 TNF antagonist naivety will be considered.

The following variables will be collected at baseline and every follow-up visit thereafter during the study period.

*\*Window period for each follow up visit will be  $\pm 1$  week*

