**11.2 Product Complaint**

**11.2.1 Definition**

A Product Complaint is any Complaint (see Section 11.0 for the definition) related to the biologic or drug component of the product or to the medical device component(s).

For a product this may include, but is not limited to, damaged/broken product or packaging, product appearance whose color/markings do not match the labeling, labeling discrepancies/inadequacies in the labeling/instructions (example: printing illegible), missing components/product, device not working properly, or packaging issues.

For medical devices, a product complaint also includes all deaths of a patient using the device, any illness, injury, or adverse event in the proximity of the device, an adverse event that could be a result of using the device, any event needing medical or surgical intervention including hospitalization while using the device and use errors.

Any information available to help in the determination of causality by the device to the events outlined directly above should be captured.

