6.4 Safety Endpoint Analysis Method

6.4.1 Adverse Events (AEs)

The AE status for each of the following items is presented in a summary table. In the summary table, the number of subjects with AE, incidence rate (%), 95% confidence interval for the incidence rate, and number of events will be included.

- AEs that caused discontinuation of the study drug
- Adverse drug reactions (ADRs)^a that caused discontinuation of the study drug
- Serious adverse events (SAEs) that caused discontinuation of the study drug
- Serious adverse drug reactions (SADRs)^a that caused discontinuation of the study drug
- SAEs that occurred during the entire study period

| dreamcis ATIGERMED COMPANY | | Last Update Date |
|----------------------------------|--|---------------------------------------|
| | CONFIDENTIAL: | · · · · · · · · · · · · · · · · · · · |
| | THIS DOCUMENT AND THE INFORMATION CONTAINED HEREIN ARE | 02-NOV-2018 |
| A LIGERMED COMPANY | PROPRIETARY TO THE COMPANY AND ARE NOT TO BE DISCLOSED WITHOUT THE WRITTEN PERMISSION OF THE COMPANY | 02-1NO V-2018 |
| | WITHOUT THE WRITTEN PERMISSION OF THE COMPANY. | |
| STATISTICAL ANALYSIS PLAN (V2.0) | | |

For the following items, the AE status will be presented in detail. Using MedDRA, the number of subjects, incidence rate (%), 95% confidence interval for the incidence rate, and number of events will be included by SOC and PT. Here, even if two or more events occurred in one subject, if they fall under one category, they will be analyzed as one subject in the category. Also, one subject may be presented as a duplicate in different AE categories.

- AEs that caused discontinuation of the study drug
- ADRs^a that caused discontinuation of the study drug
- SAEs that caused discontinuation of the study drug
- SADRs^a that caused discontinuation of the study drug
- SAEs that occurred during the entire study period

For the AEs that caused discontinuation of the study drug, the number of events for the AE items below will be presented.

- Severity
- Outcome
- Causality

As for "severity" and "causality" among the AE items, the AE status will be presented in detail. Using MedDRA, the number of subjects, incidence rate (%), and number of events will be included by SOC and PT. Here, even if two or more events occurred in one subject, if they fall under one category, they will be analyzed as one subject in the category. Also, one subject may be presented as a duplicate in different AE categories.

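### Protocol 11.1.5 and 9.7.1 conflict on collecting non-serious AEs that stop adalimumab, and 9.2.2 cuts off their outcome, so 12 of 22 listed SAP 6.4.1 outputs can be incomplete

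*Protocol*

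**What the plan says.** **Solicitation.** Protocol 11.1.5 sets two rules. For serious events: "This protocol requires all SAEs as outlined in protocol section 11.1.1 to be actively solicited". For the rest: "non-serious events will not be actively solicited as these events are not likely to contribute", followed by "Any non-serious AEs will be collected as spontaneous reports if AbbVie is notified". It makes no exception for an event that leads to stopping the drug.

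**Analysis in the protocol.** Protocol 9.7.1 adds, without limiting it to serious events: "AEs leading to discontinuation of adalimumab will be collected and tabulated".

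**Drop-out.** Under Protocol 9.2.2, discontinuing adalimumab at any point is itself a reason for drop-out, and "Once a subject is dropped out from the study, no further information for that subject will be collected". The exceptions are the reason for drop-out and SAEs up to 70 days after the last dose. Protocol 9.1 nevertheless gives all subjects one safety follow-up about 70 days after the last dose.

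**Stopping reason.** Protocol 9.3 (Blood samples) says: "In the event of adalimumab discontinuation, the reason for discontinuation will be collected". SAP 6.2 includes adverse event among the reasons for stopping the drug.

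**Analysis in the SAP.** SAP 6.4.1 requires AEs causing discontinuation in summary and SOC/PT tables with 95% confidence intervals, as a rate per 100 PTYs, and in listings. It also states: "For the AEs that caused discontinuation of the study drug, the number of events for the AE items below will be presented". Those items are severity, outcome and causality.

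**The concern.** Take a subject who stops adalimumab because of a non-serious reaction. A site working from 9.7.1 would seek out the event and record it. A site working from 11.1.5 would not ask, and the sponsor would learn of it only if someone volunteered a report. Both sites would be following the protocol. At either site, 9.2.2 ends collection once the drug is stopped, so how a non-serious event resolved need not be recorded.

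The SAP then pools serious events, which are solicited, with non-serious events, which may not be. It divides the event count by person-time summed over all subjects, and it attaches confidence intervals to the incidence percentages. A reader of those tables would assume uniform ascertainment. Any error from incomplete capture runs one way: adalimumab would appear better tolerated than it was. Differences between sites could also reflect which section each one followed.

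**Working it through.** The plan gives no expected frequency for AEs leading to discontinuation, so it has no figure of its own to reproduce here. The check has three parts.

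**1. What is recorded for a non-serious AE that stops the drug**

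- That the subject stopped, and why: yes (Protocol 9.3 and 9.2.2; SAP 6.2). The SAP 6.2 list of reasons for leaving the study has no adverse event category, but its list of reasons for stopping the drug does.
- Event term: required if 9.7.1 governs; only if volunteered if 11.1.5 governs.
- Severity: Protocol 11.1.2 defines grades for AEs collected as a data point and for all SAEs. Whether this AE is a data point again depends on which section governs.
- Causality: Protocol 11.1.3 has two categories. The SAP's ADR definition uses a graded scale, counting four of its grades as ADRs, so the two documents do not match.
- Outcome: after discontinuation, 9.2.2 keeps only the reason and SAEs. One can reconcile 9.1 with 9.2.2 by reading the 70-day contact as an SAE check only, but then the outcome of a non-serious event is not obtained.

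**2. How many SAP 6.4.1 outputs are exposed**

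Each listed item is counted once. An item is exposed if it concerns AEs or ADRs causing discontinuation, which need not be serious. The later severity and causality breakdown by SOC/PT is read as applying to AEs causing discontinuation, since it follows directly from that list.

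| Output block | Items | Exposed |
|---|---|---|
| Summary table | 5 | 2 |
| By SOC and PT | 5 | 2 |
| Event counts: severity, outcome, causality | 3 | 3 |
| Severity and causality by SOC and PT | 2 | 2 |
| Rate per 100 PTYs | 2 | 1 |
| Subject listings | 5 | 2 |
| **Total** | **22** | **12** |

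12 / 22 = 55%. The other 10 rest on solicited data: 7 concern serious AEs or ADRs causing discontinuation, and 3 concern SAEs over the whole study.

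**3. What governs the size**

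Let s be the non-serious share of AEs causing discontinuation and c the fraction of those captured, with serious events fully captured. Then

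observed / true = (1 − s) + s × c.

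The documents give neither s nor c. For illustration only, assume s = 0.3 to 0.7, c = 0.5 to 1.0, and a true risk of 5% in the planned 147 subjects (147 × 0.05 = 7.35 subjects):

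- s = 0.7, c = 0.5: 0.30 + 0.35 = 0.65, or 4.8 subjects observed.
- s = 0.3, c = 0.5: 0.70 + 0.15 = 0.85, or 6.2 subjects.
- s = 0.7, c = 0.8: 0.30 + 0.56 = 0.86, or 6.3 subjects.
- s = 0.3, c = 0.8: 0.70 + 0.24 = 0.94, or 6.9 subjects.
- c = 1 (every site follows 9.7.1): 1.00, no under-count at any s.

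The ratio does not depend on the assumed 5%.

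**The case against.** The best defence is that the specific rule overrides the general one. Section 9.7.1 addresses exactly this class of event and says it is to be collected; 11.1.5 is a general statement in a section on SAE reporting, and its selective approach is declared and justified there. The case report form is not among the documents and may well hold an AE page with these fields; the SAP's graded causality scale suggests so without proving it. Nor does the absence of an AE item from the 9.3 visit lists show much, because SAEs and the 70-day follow-up are missing from those lists too. All this stands, and it is why the finding is a conflict to resolve rather than an absence of collection. It does not settle the matter: 11.1.5 also uses the language of collection, and there it means spontaneous reports, so a site can read 9.7.1 as tabulating whatever arrives.

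Two further readings are tempting and should be resisted.

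- A reader might infer that 9.2.2 removes the event from the count. It does not. The AE precedes the drop-out that it triggers, and the reason is kept. What can be lost is later follow-up, mainly outcome.
- A reader might see Protocol 11.2 as a third conflicting rule, because a product complaint includes "an adverse event that could be a result of using the device". It is not one: reporting an event that the site already knows of is compatible with not soliciting such events.

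**Conclusion.** The conflict between 11.1.5 and 9.7.1 is plain on the text, and 9.2.2 is not reconciled with the 70-day safety follow-up in 9.1. Twelve of 22 listed outputs in SAP 6.4.1 depend on events caught in that conflict. Where sites follow 11.1.5, these counts and rates can be understated; under 9.2.2, outcomes of non-serious events can be missing.

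A reader might go further and conclude that AE discontinuations will be under-counted. The documents do not support that. The result depends on site practice, which they do not describe, and the illustrated range runs from 65% of the true count to no loss at all. Nor may a capture fraction for spontaneous reports be applied to the whole count, since the serious part is actively solicited. The conclusion rests on the wording of the two documents without sight of the case report form. It deserves correction because the possible error has one direction and the remedy is cheap.

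**What to change.** 1. **Protocol 11.1.5:** add an exception that any AE leading to discontinuation of adalimumab, serious or not, is actively solicited and recorded with term, onset, severity, causality and outcome.
2. **Protocol 9.2.2:** add to the exceptions any AE that led to discontinuation, followed for outcome to the 70-day follow-up. This also reconciles 9.2.2 with 9.1.
3. **Protocol 9.3:** add the item to the data lists, including the 70-day follow-up.

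The milestones put the end of data collection in 2Q 2017 and SAP V2.0 is dated 02-NOV-2018, so collection may already have closed. In that case, **SAP 6.4.1** should compare subjects whose recorded reason for stopping the drug is an adverse event with subjects who have an AE record marked as causing discontinuation, and report how many do not match. It should label the non-serious part of these tables and rates as possibly incomplete because it was not actively solicited. The comparison checks subjects, not events, and cannot recover missing severity, causality or outcome.

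The cost is a wording amendment and a little more site data entry. No visit is added, because 9.1 already provides the 70-day follow-up, and no treatment rule changes.
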